### **18.2.2. Source Data**

Source data is defined as all information in original records and certified copies of original records of clinical findings, observations, or other activities in a clinical trial necessary for the reconstruction and evaluation of the trial. Source data should be accurate, legible, contemporaneous, original, attributable, complete and consistent. Source data is documented in source documents which may be both electronic and on paper.

The Investigator(s) should be aware about the location of the source data and consistent in recording them. The intended location should be clearly defined prior to subject enrollment. One way of achieving this is to generate a source data location list. The source data location list will be prepared by the site and will be signed and dated by the Principal Investigator. The list will be filed in the Investigator's trial master file.

### **18.2.3. Data Collection**

The Principal Investigator must maintain detailed records on all subjects who provide informed consent. Data for screened and randomized subjects will be entered into eCRFs. eCRFs should be completed within 3 business days of each subject visit as much as possible. Review of the eCRFs will be completed remotely by Santen (or designee). At designated intervals, a study monitor will perform Source Data Verification on site. During those visits, Santen (or designee) will monitor the subject data recorded in the eCRF against source documents at the study site. Santen (or designee) will review and evaluate eCRF data and use standard system edits, and may use centralized monitoring evaluations, to detect errors in data collection. At the end of the study, a copy of the completed eCRFs will be sent to the site to be maintained as study records.

## **19. PUBLICATION POLICY**

The existence of this clinical study is confidential, and it should not be discussed with persons outside of the study. Additionally, the information in this document and regarding this study contains trade secrets and commercially sensitive information that is confidential and may not be disclosed unless such disclosure is required by federal or state law or regulations. Subject to the foregoing, this information may be disclosed only to those persons involved in the study who have a need to know, but all such persons must be instructed not to further disseminate this information to others. These restrictions of disclosure will apply equally to all future information supplied that is indicated as confidential. Information pertaining to this study will be published on [www.clinicaltrials.gov](http://www.clinicaltrials.gov).

The data generated by this clinical study are the property of Santen and should not be disclosed without the prior written permission of Santen. These data may be used by Santen now and in the future for presentation or publication at Santen's discretion or for submission to governmental regulatory agencies. Santen reserves the right of prior review of any publication or presentation of data from this study.

In signing this protocol, the Principal Investigator agrees to the release of the data from this study, and acknowledges the above publication policy.

## 21. APPENDICES

### 21.1. Appendix A - Obligations of Investigators

In summary, the Principal Investigator has agreed to the following obligations:

- Obtaining informed consent from every subject before the subject's participation in any study-related activity and maintaining records of consent as part of the study records.
  - Obtaining approval from the IRB or IEC before involving any subject in any study-related activity; submitting verification of the approval to Santen; submitting periodic progress reports (at least annually) and final report to IRB or IEC.
  - Approving the protocol and conducting the study according to the protocol and applicable regulations; informing Santen of all deviations from the protocol.
  - Informing the IRB or IEC of all protocol amendments/modifications; sending Santen a copy of the letter from the IRB or IEC approving the amendment/modification.
  - Reporting to Santen any AEs and reporting to the IRB or IEC any reportable AEs that occur in the course of the investigation.
  - Keeping careful and accurate records of all clinical study data (study records must be considerably more exact and complete than those kept in ordinary medical practice); maintaining records of all materials submitted to the IRB or IEC and of all action by the IRB or IEC regarding the study.
  - Making study records available for inspection by Santen and representatives of regulatory agencies and the IRB or IEC; keeping records until notified by Santen that they may be destroyed.
  - Maintaining proper control and documentation of all test and control articles.
  - Submitting the following records and reporting to Santen. See I, II, and III as listed below.
- I. Before the Beginning of the Study Providing Santen the following:
    - A signed Form FDA 1572, Statement of Investigator, if applicable.
    - A signed Financial Disclosure Form.
    - A current Curriculum Vitae (CV) if not submitted to Santen previously or if updated.
    - CVs for all Sub-Investigators.
    - A letter from the IRB or IEC indicating that the protocol was approved, including the name and address of the IRB or IEC.
    - A copy of the consent form approved by the IRB or IEC.
    - A list of current members of the IRB or IEC.

- A copy of the source data location list.
  - A copy of delegation list/log.
  - A copy of training log.
- II. While the Study is in Progress
- Acknowledgment of receipt of the test and control articles; documentation of disposition of all test and control articles.
  - eCRFs for each subject enrolled in the study.
  - Information regarding all deviations from the protocol.
  - Information regarding all AEs occurring to a subject while enrolled in the study.
  - Annual progress report (if study is on-going for more than one year). Letter from the IRB or IEC indicating approval of the annual progress report.
- III. Once the Study is Completed
- Disposition of all used and/or unused test and control articles, as well as documentation of all drug accountability.
  - Providing Santen a final study report.

## 21.2. Appendix B - Elements of Informed Consent

### I. Elements of Informed Consent

The following information must be provided to each subject in obtaining informed consent as required by ICH-GCP and/or local regulations. If written consent is being obtained, the subject (or subject's legal representative) should be provided with a copy of the signed written ICF.

- A. The trial involves research.
- B. The purpose of the trial.
- C. Name of the Investigator (s) and IRB/IEC
- D. The trial treatment(s) and the probability for random assignment to each treatment.
- E. The trial procedures to be followed, including all invasive procedures.
- F. The subject's responsibilities.
- G. Those aspects of the trial that are experimental.
- H. The reasonably foreseeable risks or inconveniences to the subject and, when applicable, to an embryo, fetus, or nursing infant.
- I. The reasonably expected benefits. When there is no intended clinical benefit to the subject, the subject should be made aware of this.
- J. The alternative procedure(s) or course(s) of treatment that may be available to the subject, and their important potential benefits and risks.
- K. The compensation and/or treatment available to the subject in the event of trial-related injury.
- L. The anticipated prorated payment, if any, to the subject for participating in the trial.
- M. The anticipated expenses, if any, to the subject for participating in the trial.
- N. That the subject's participation in the trial is voluntary and that the subject may refuse to participate or withdraw from the trial, at any time, without penalty or loss of benefits to which the subject is otherwise entitled.
- O. That the monitor(s), the auditor(s), the IRB/IEC, and the regulatory authority(ies) will be granted direct access to the subject's original medical records for verification of clinical trial procedures and/or data, without violating the confidentiality of the subject, to the extent permitted by the applicable laws and regulations and that, by signing a written informed consent form, the subject or the subject's legally acceptable representative is authorizing such access.
- P. That records identifying the subject will be kept confidential and, to the extent permitted by the applicable laws and/or regulations, will not be made publicly available. If the results of the trial are published, the subject's identity will remain confidential.

- Q. That the subject or the subject's legally acceptable representative will be informed in a timely manner if information becomes available that may be relevant to the subject's willingness to continue participation in the trial.
- R. The person(s) to contact for further information regarding the trial and the rights of trial subjects, and whom to contact in the event of trial-related injury.
- S. The foreseeable circumstances and/or reasons under which the subject's participation in the trial may be terminated.
- T. The expected duration of the subject's participation in the trial.
- U. The approximate number of subjects involved in the trial.
- V. Clinical trial information has been or will be available on <http://www.clinicaltrials.gov>.

## II. Additional Elements of Informed Consent for Optional Future Pharmacogenomics/genomics Laboratory Research Study

The following information must be provided to each subject in obtaining informed consent for the future pharmacogenomics/genomics laboratory research study:

- 1. The location of storage of their sample.
- 2. The duration of storage of their sample.
- 3. What group(s) within Santen will be using their sample in research study.
- 4. What use restrictions are assigned to their sample.
- 5. Destruction of their sample if they withdraw prior to its use, and retention of the sample data if they withdraw after its use.

The informed consent requirements in this protocol are not intended to preempt any applicable local laws which require additional information to be disclosed for informed consent to be legally effective.

Nothing in this protocol is intended to limit the authority of a physician to provide emergency medical care to the extent the physician is permitted to do so under applicable local laws.

## 21.3. Appendix C - Procedures for Assessments

**The following descriptions are for adult and pediatric subjects, however specific guidance for pediatric subjects is shown in Section 21.4.**

### 21.3.1. Demographics, Medication/Therapy and Medical History

Demographics including age, sex, race, prostaglandin analogs naïve status, and ethnicity will be obtained through subject interviews at Visit 1 (Screening).

Medications and procedures/therapies will be confirmed through subject interviews during the study.

Following details of prior medication that has been used for glaucoma or OHT within 28 days before the date of Visit 1, or any concomitant medication, must be recorded in the subject's source documents.

- Name of medication, route of administration, treated eye(s) (if applicable), dose, frequency, indication, start date and stop date

Following details of prior procedure/therapy that has been received for glaucoma or OHT within 28 days before the date of Visit 1, or any concomitant procedure/therapy, must be recorded in the subject's source documents.

- Name of procedure/therapy, treated eye(s) (if applicable), indication, start date and stop date

Medical history including all lifetime ocular medical history to the extent possible, non-ocular medical history within 5 years, diagnosis, ocular surgical history, current ocular and systemic conditions will be confirmed through subject interviews at Visit 1 (Screening) to determine if the subject meets eligibility criteria. Primary diagnosis and the affected eye must be recorded in the subject's source documents.

- Name of concurrent disease and affected eye(s) (if applicable) will be confirmed at Visit 1 (Screening) and Visit 2 (Baseline), and recorded in the subject's source documents.

### 21.3.2. Pregnancy Test

A urine pregnancy test will be conducted using a commercially available test kit at Visit 1 (Screening), Visit 2 (Baseline), and Visit 5 Study Exit/Early Termination for all females of childbearing potential. A female is considered of childbearing potential unless she is post-menopausal (at least 12 months since last menses occurred), is without a uterus or without both ovaries, or has had a bilateral tubal ligation. To perform the pregnancy test, follow instructions provided by the manufacturer of the urine pregnancy test kit.

[figure not shown]

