#### **Inclusion Criteria for ADULT subjects:**

At Visit 1 (Screening), the subjects must meet all of the following inclusion criteria:

1. Provide signed written informed consent on the Institutional Review Board (IRB)/Ethics Committee (EC) approved Informed Consent Form (ICF).
2. Be 18 years of age or older on the date of signing the ICF and be able and willing to comply with all treatment and follow-up study procedures.
3. If a subject is a female of childbearing potential (i.e., not post-menopausal [within 12 months since the last menses] or not surgically sterile [less than 6 months from date of

surgery]), she must have a negative urine pregnancy test and must use at least one of the following acceptable contraceptive methods during the study (as well as for 4 weeks following last dose in study).

- Abstinence
- Hormonal contraceptive method (including oral or transdermal contraceptives, injectable progesterone, progestin subdermal implants, progesterone-releasing intrauterine devices [IUDs]) initiated at least 28 days prior
- Placement of a copper-containing IUD
- Condom with spermicidal foam/gel/film/cream/suppository
- Vasectomized male partner (surgery at least 6 months prior)

Male subjects capable of fathering children should use/ practice an acceptable contraceptive method, such as abstinence, condom or vasectomy (surgery at least 6 months prior) or other contraceptive method deemed adequate by the investigator throughout the course of the study (as well as for 12 weeks following last dose in study).

4. Must have a diagnosis of OAG (including Pigmentary Glaucoma or Pseudoexfoliative Glaucoma) or OHT in both eyes, or one eye with OAG and the other with OHT.
5. BCVA of  $+0.60$  logMAR (Snellen equivalent 20/80) or better in each eye.
6. Central corneal thickness  $\geq 480$   $\mu\text{m}$  and  $\leq 600$   $\mu\text{m}$  in each eye.
7. Anterior chamber angle grade  $\geq 2$  (Shaffer scale) in each eye.

In addition to continuing to meet inclusion criterion 5 (BCVA), the subject must meet the following criteria at Visit 2 (Baseline, Day 1):

8. Completed the required wait/washout period.
9. At all time points of IOP measurements (08:00, 10:00 and 16:00) at Visit 2 (Baseline, Day 1), have IOP of  $\geq 22$  mmHg in at least one eye (the same eye), and  $\leq 34$  mmHg in both eyes.

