## 7. INVESTIGATIONAL PLAN

### 7.1. Overall Study Design

This is a Phase III, randomized, double-masked, active-controlled, parallel-group and multi-center study investigating the efficacy and safety of DE-117 Ophthalmic Solution 0.002% in subjects with glaucoma or OHT.

[figure not shown]
See the study design diagram in [Figure 1](#). This study will consist of a Screening Period of up to 35 days including a washout period of up to 28 days (+ 7 days window) and a 3-month Double-Masked Treatment Period.

Approximately 400 adult subjects and up to 30 pediatric subjects with glaucoma or OHT who meet all eligibility criteria will be randomized in a 1:1 ratio to receive either:

- DE-117 Ophthalmic Solution 0.002% QD (20:00) and Vehicle QD (08:00), or
- Timolol Maleate Ophthalmic Solution 0.5% BID (20:00 & 08:00).

In the Double-Masked Treatment Period, Timolol Maleate Ophthalmic Solution 0.5% will be used as active control.

**Figure 1:** Study Design

At the Screening visit (Visit 1), subjects will be screened against the inclusion and exclusion criteria. Eligible subjects will be instructed to discontinue use of all IOP-lowering medications, if any, during a washout period as follows (up to +7 days as a window is allowed):

- Miotics: 7 days
- Oral/topical Carbonic Anhydrase Inhibitors (CAIs): 7 days

- Alpha agonists: 14 days
- Alpha/beta agonists: 14 days
- Alpha antagonists ( $\alpha$ 1 blocker): 28 days
- Beta antagonists ( $\beta$  blocker, including  $\alpha\beta$  blockers): 28 days
- Prostaglandin Analogs (PGA): 28 days
- Rho kinase inhibitor: 28 days
- Combination drugs: The longest washout period of the individual component will be used.

During the required washout period, subjects who discontinue their current treatment may, if the Investigator deems it necessary, be treated with a short-acting IOP lowering agent, topical CAI, e.g., brinzolamide or dorzolamide eye drops, one drop twice daily. Topical CAI treatment must be stopped 1 week before the randomization at Visit 2 (Baseline, Day 1). An interim safety visit during the washout period (mid-washout visit; Visit 1a) may be performed during the washout period if, in the Investigator's opinion, a subject's IOP may be of concern during the washout period. If subjects are treated with a topical CAI during the washout period, mid-washout visit (Visit 1a) is recommended to be performed.

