## 7.4. Schedule of Events and Procedures

**Table 3: Schedule of Events and Procedures for ADULT subjects**

	Washout Period		Double-Masked Treatment Period			
	Visit 1 Screening	Washout Period (up to 4 weeks) Optional Visit 1a	Visit 2 Eligibility/Basel ine (Day 1)	Visit 3 Week 1 (Day 8±2)	Visit 4 Week 6 (Day 43 ±3)	Visit 5 Month 3 (Day 91±7) Exit or Early Termination n
Informed Consent(s) including the optional consent for pharmacogenomics/ genomics laboratory research study a	X					
Inclusion/Exclusion Criteria	X		X			
Demographics and Medical History, including prior PGA b	X					
Concomitant Medications/ Therapies	X	X	X	X	X	X
Dosing Compliance				X	X	X
AEs		X	X	X	X	X
Pregnancy Test c	X		X			X
Vital Signs (blood pressure/pulse rate) d	X		X (08:00)			X (08:00)
Refraction e	X					
BCVA e	X	X	X (08:00)	X (08:00)	X (08:00)	X (08:00)
Biomicroscopy f	X	X	X (08:00)	X (08:00)	X (08:00)	X (08:00)
IOP g	X	X	08:00 10:00 16:00	08:00 10:00 16:00	08:00 10:00 16:00	08:00 10:00 16:00
Pachymetry h	X					
Instill study medication after IOP measurement				X (08:00)	X (08:00)	X (08:00)
Iris color, eyelash, eyelid i			X (photo)			X (photo)
Gonioscopy j	X					
Visual Field k	X					
Ophthalmoscopy l	X (pupil dilation)		X (16:00)			X (16:00, pupil dilation)
Blood Sampling for Pharmacogenomics/genomics m				X		
Dispense Study Medication			X		X	
Collect Study Medication					X	X
Phone call to remind subject to take evening dose on the day before each visit				X	X	X

- a. Informed Consent Form must be signed and dated before study procedures are performed. Informed consent for the optional pharmacogenomics/genomics laboratory research study may be obtained at any visit prior to study exit.
- b. Prostaglandin naive subjects are defined as subjects who are not known to have used prostaglandin as their glaucoma treatment. The previous use of prostaglandin should be confirmed by either subject's medical records or subject history.
- c. A urine pregnancy test will be conducted for all female subjects of childbearing potential.
- d. Vital signs (resting blood pressure and pulse rate) will be collected in sitting position anytime at Visit 1 (Screening), and approximately 08:00 for Visit 2 (Baseline), and Visit 5 before the morning dose.

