## 8. SELECTION AND WITHDRAWAL OF SUBJECTS

Subjects must meet all eligibility (inclusion and exclusion) criteria.

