### 8.1. Subject Inclusion Criteria for ADULT Subjects

#### Inclusion Criteria Specific for ADULT Subjects:

At Visit 1 (Screening), the subjects must meet all of the following inclusion criteria:

1. Provide signed written informed consent on the Institutional Review Board (IRB)/Ethics Committee (EC) approved Informed Consent Form (ICF).
2. Be 18 years of age or older on the date of signing the ICF and be able and willing to comply with all treatment and follow-up study procedures.
3. If a subject is a female of childbearing potential (i.e., not post-menopausal [within 12 months since the last menses] or not surgically sterile [less than 6 months from date of surgery]), she must have a negative urine pregnancy test and must use at least one of the following acceptable contraceptive methods during the study (as well as for 4 weeks following last dose in study).
  - Abstinence
  - Hormonal contraceptive method (including oral or transdermal contraceptives, injectable progesterone, progestin subdermal implants, progesterone-releasing intrauterine devices [IUDs]) initiated at least 28 days prior
  - Placement of a copper-containing IUD
  - Condom with spermicidal foam/gel/film/cream/suppository
  - Vasectomized male partner (surgery at least 6 months prior)

Male subjects capable of fathering children should use/ practice an acceptable contraceptive method, such as abstinence, condom or vasectomy (surgery at least 6 months prior) or other contraceptive method deemed adequate by the investigator throughout the course of the study (as well as for 12 weeks following last dose in study).

4. Must have a diagnosis of OAG (including Pigmentary Glaucoma or Pseudoexfoliative Glaucoma) or OHT in both eyes, or one eye with OAG and the other with OHT.
5. BCVA of +0.60 logMAR (Snellen equivalent 20/80) or better in each eye.
6. Central corneal thickness  $\geq 480 \mu\text{m}$  and  $\leq 600 \mu\text{m}$  in each eye.
7. Anterior chamber angle grade  $\geq 2$  (Shaffer scale) in each eye.

In addition to continuing to meet inclusion criterion 5 (BCVA), the subject must meet the following criteria at Visit 2 (Baseline, Day 1):

8. Completed the required wait/washout period.

9. At all time points of IOP measurements (08:00, 10:00 and 16:00) at Visit 2 (Baseline, Day 1), have IOP of  $\geq 22$  mmHg in at least one eye (the same eye), and  $\leq 34$  mmHg in both eyes.

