#### General

1. Females who are pregnant, nursing or planning a pregnancy.
2. Subjects with known or suspected drug or alcohol abuse.
3. Current or planned participation in any other clinical trial involving an investigational product or device within 4 weeks prior to Visit 1 (Screening) or at any time during this trial.
4. Subjects who have been exposed to DE-117 prior to Visit 1 (Screening).

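### Protocol 21.3.2 exempts every woman with a tubal ligation from pregnancy testing, while adult inclusion 3 requires a negative Visit 1 test if sterilising surgery was less than 6 months ago

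*Protocol*

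**What the plan says.** **Eligibility text.** Adult inclusion criterion 3 (protocol synopsis and section 8.1) includes among women of childbearing potential those who are "not surgically sterile [less than 6 months from date of surgery"; it requires of them a negative urine test and contraception. It belongs to the list introduced by "At Visit 1 (Screening), the subjects must meet all of the following inclusion criteria". Section 8 adds: "Subjects must meet all eligibility (inclusion and exclusion) criteria".

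**Procedures text.** Section 21.3.2 (Appendix C) places the urine test at Visits 1, 2 and 5 for women of childbearing potential. It removes from that group a woman who is at least 12 months post-menopausal, or who "is without a uterus or without both ovaries, or has had a bilateral tubal ligation". No time since surgery is attached. Section 21.3 says that Appendix C serves adult and pediatric subjects alike.

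**Schedule.** Note c to Table 3 says: "A urine pregnancy test will be conducted for all female subjects of childbearing potential". Neither the note nor the visit lists in sections 7.4.1, 7.4.3 and 7.4.6 define the term.

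**Contraception.** Inclusion 3 makes it mandatory for women until 4 weeks after the last dose. Section 12.1.3 requires it during the study and only recommends the following 4 weeks, counted from study completion.

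**The concern.** The two definitions give opposite instructions for one kind of participant: a pre-menopausal adult whose tubes were ligated less than 6 months before screening. Under inclusion 3 she cannot enter without a negative test. Under 21.3.2 she is not in the group to be tested. Appendix C is the procedures text for this test, so a site could reasonably take its definition from there and miss an entry requirement while believing that it had followed the protocol. What is at stake is compliance with an eligibility criterion, and a small safety margin for a very small group.

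**Working it through.** The plan states no figure on this point, so the check is a comparison of texts, followed by visit-window arithmetic.

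**Worked case.** Take a pre-menopausal adult 3 months after bilateral tubal ligation at Visit 1.
- Inclusion 3: 3 months is less than 6, so she is of childbearing potential and needs a negative test at Visit 1.
- 21.3.2: she has had a ligation, so she is exempt and no test is scheduled at Visit 1, 2 or 5.
- At 6 months or more after surgery, the two texts agree on the natural reading of inclusion 3.

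**Is ligation within inclusion 3?** The criterion speaks of surgical sterility and does not name the operation. Ligation is the natural reading. A waiting time has little purpose once the uterus or both ovaries are gone, and the same criterion asks for at least 6 months since a partner's vasectomy.

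**Two further mismatches within inclusion 3.** Word for word, it also covers a woman 3 months after hysterectomy or removal of both ovaries, whom 21.3.2 exempts. It also joins its two conditions with *or*, so that literally a pre-menopausal woman stays of childbearing potential even years after sterilisation. Editing 21.3.2 alone would leave both in place.

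**Which tests are at stake?** Inclusion 3 applies at Visit 1. At Visit 2, section 8.1 asks only that criterion 5 (visual acuity) continue to be met, alongside criteria 8 and 9. The one test that eligibility requires is therefore the Visit 1 test. The Visit 2 and Visit 5 tests come from the schedule and 21.3.2, and would apply to her only under an aligned definition.

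**When would an aligned definition still cover her?** Let d be the days since ligation at Visit 1, and take 6 months as 183 days (an assumption; the calendar range is 181 to 184).
- Visit 1 to Visit 2: 1 to 35 days (section 7.1).
- Visit 2 (Day 1) to Visit 5 (Day 84 to 98): 83 to 97 days.
- Visit 1 to Visit 5: 1 + 83 = 84 to 35 + 97 = 132 days.
- Covered at Visit 2 if d < 183 − 35 = 148 (longest gap) up to d < 183 − 1 = 182 (shortest gap).
- Covered at Visit 5, for completers, if d < 183 − 132 = 51 up to d < 183 − 84 = 99.

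Examples with a 28-day gap and Visit 5 on Day 91, which is 90 days after Visit 2:

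| d at Visit 1 | Days since ligation at Visit 2 | At Visit 5 | Tests under the aligned definition |
|---|---|---|---|
| 61 | 89 | 179 | 3 |
| 122 | 150 | 240 | 2 |
| 168 | 196 | 286 | 1 |

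**Contraception.** For a completer with last dose and exit on Day 91, both texts end on 91 + 28 = Day 119, so only the force of the instruction differs. For a woman who stops drug early but stays in follow-up, the advice in 12.1.3 ends later than the requirement in inclusion 3.

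**The case against.** The strongest reply is that the protocol already protects against this. Section 8 makes every criterion binding, and inclusion 3 itself demands the test. Criteria are reviewed at Visits 1 and 2, and exclusion 1 bars "Females who are pregnant, nursing or planning a pregnancy" at both. Section 21.3.2 forbids no test, so a site applying inclusion 3 as written would do one. All of this stands, and it makes the safety gain small. It does not remove the conflict: a site that uses the 21.3.2 definition during its eligibility review would see no missing test, and for that woman the pregnancy exclusion would rest on other information.

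A reader might infer more than the documents support:
- *That pregnant women could enter unchecked, or that harm is shown.* Section 12.1.3 reports that there are no controlled data in human pregnancy, which is missing knowledge, and the controls above remain.
- *That the Visit 2 and Visit 5 tests are also breached.* Inclusion 3 does not reach those visits, and under 21.3.2 no test is due for her.
- *That the number of missed tests can be estimated.* No document says how many women had a recent ligation.
- *That the records check needs no further data.* Section 21.3.1 collects 5 years of non-ocular medical history but does not expressly require dates of non-ocular surgery. SAP Table 5 anticipates partial dates and sets a year-only onset to the first day of that year, which can make a recent operation look older than 6 months.

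**Conclusion.** The point holds as a minor internal inconsistency in current protocol text. A site following 21.3.2 would omit a Visit 1 test that inclusion 3 requires for a woman less than 6 months from tubal ligation, and nothing in the protocol settles which definition governs. Very few women are affected, possibly none. For each, the loss is 1 required entry test, with 0 to 2 further tests depending on how long an aligned definition would cover her. The conclusion rests on reading surgical sterility in inclusion 3 as including ligation; the day cut-offs rest on 183 days for 6 months. Power, endpoints and analyses are unaffected. The contraception mismatch in 12.1.3 is secondary, since inclusion 3 still binds.

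**What to change.** **Use one definition in both places.**
- In 21.3.2, limit the ligation exemption to operations done at least 6 months earlier. Keep the exemption for an absent uterus or both ovaries absent, where a test would serve no purpose.
- In inclusion 3 (synopsis and section 8.1), state that a female is of childbearing potential unless she is at least 12 months post-menopausal, lacks a uterus or both ovaries, or had a bilateral tubal ligation at least 6 months earlier. This also removes the difficulty with *or*.
- Keep the full definition in 21.3.2 and do not replace it with a pointer to the adult criterion: pediatric criterion 4 has no definition of its own.

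**Secondary, in 12.1.3.** Make the 4 weeks after the last dose required for women, to match inclusion 3. Keep the existing advice that runs to 4 weeks after study completion, so that nothing is shortened for women who stop drug early but stay in follow-up.

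**For this trial.** SAP section 3.1 says that enrolment had completed, so new wording changes no entry test here and helps only if the text is reused. Check surgical history against pregnancy test records, going to source documents where the operation date is missing or partial. List any missed entry test under the Inclusion/Exclusion Criteria category of SAP section 7.4.

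**Cost.** A few clauses of protocol text, 1 to 3 urine tests per affected woman with kits that the sponsor already supplies (section 10.8), and one records check with some source review.
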